### **Scaling (applicable only for irradiated lesions/lesion intervention)**

If  $> 1/3$  of target lesion measurements are treated as missing (because of intervention) then target lesion response will be NE, unless the sum of diameters of non-missing target lesion would result in PD (i.e. if using a value of 0 for missing lesions, the sum of diameters has still increased by 20% or more compared to nadir and the sum of target lesions has increased by 5 mm from nadir).

If  $\leq 1/3$  of the target lesion measurements are treated as missing (because of intervention) then the results will be scaled up (based on the sizes at the nadir visit to give an estimated sum of diameters and this will be used in calculations; this is equivalent to comparing the visit sum of diameters of the non-missing lesions to the nadir sum of diameters excluding the lesions with missing measurements).

### Example of scaling

Lesion	Longest diameter at nadir visit	Longest diameter at follow-up visit
1	7.2	7.1
2	6.7	6.4
3	4.3	4.0
4	8.6	8.5
5	2.5	Intervention
Sum	29.3	26

Lesion 5 has had an intervention at the follow-up visit.

The sum of lesions 1-4 at the follow-up is 26 cm. The sum of the corresponding lesions at baseline visit is 26.8 cm.

Scale up as follows to give an estimated TL sum of 28.4cm:

$$\frac{26}{26.8} \times 29.3 = 28.4cm$$

### Lesions that split in two or more parts

If a TL splits in two, then the LDs of the split lesions should be summed and reported as the LD for the lesion that split.

### Lesions that merge

If two or more TLs merge, then the LD of the merged lesion should be recorded for one of the TL sizes and the other TL size should be recorded as 0 mm.

### Change in method of assessment of TLs

CT and MRI are the only methods of assessment that can be used within the trial. If a change in method of assessment occurs between CT and MRI, this will be considered acceptable and no adjustment within the programming is needed.

If a change in method involves clinical examination (e.g. CT changes to clinical examination or vice versa), any affected lesions should be treated as missing.

### 3.1.2.2 Non-target lesions (NTLs) and New lesions.

At each visit an overall assessment of the NTL response should be recorded by the investigator. This section provides the definitions of the criteria used to determine and record overall response for NTL at the investigational site at each visit.

NTL response will be derived based on the investigator’s overall assessment of NTLs as follows:

**Table 8 NTL Visit Responses**

Visit Responses	Description
Complete Response (CR)	Disappearance of all NTLs present at baseline with all lymph nodes non-pathological in size (<10 mm short axis).
Progressive Disease (PD)	Unequivocal progression of existing NTLs. Unequivocal progression may be due to an important progression in one lesion only or in several lesions. In all cases the progression MUST be clinically significant for the physician to consider changing (or stopping) therapy.
Non CR/Non PD	Persistence of one or more NTLs-with no evidence of progression.
Not Evaluable (NE)	Only relevant when one or some of the NTLs were not assessed and, in the investigator's opinion, they are not able to provide an evaluable overall NTL assessment at this visit.  Note: For patients without TLs at baseline, this is relevant if any of the NTLs were not assessed at this visit and the progression criteria have not been met.
Not Applicable (NA)	Only relevant if there are no NTLs at baseline

To achieve ‘unequivocal progression’ on the basis of NTLs, there must be an overall level of substantial worsening in non-target disease such that, even in the presence of SD or PR in TLs, the overall tumor burden has increased sufficiently to merit discontinuation of therapy. A modest ‘increase’ in the size of one or more NTLs is usually not sufficient to qualify for unequivocal progression status.

Details of any new lesions will also be recorded with the date of assessment. The presence of one or more new lesions is assessed as progression.

A lesion identified at a follow up assessment in an anatomical location that was not scanned at baseline is considered a new lesion and will indicate disease progression.

The finding of a new lesion should be unequivocal: i.e., not attributable to differences in scanning technique, change in imaging modality or findings thought to represent something other than tumor.

If a new lesion is equivocal, for example because of its small size, the treatment and tumor assessments should be continued until the new lesion has been confirmed. If repeat scans confirm there is a new lesion, then the progression date should be declared using the date of the initial scan.

New lesions will be identified via a Yes/No tick box. The absence and presence of new lesions at each visit should be listed alongside the TL and NTL visit responses.

A new lesion indicates progression so the overall visit response will be PD irrespective of the TL and NTL response.

If the question ‘Any new lesions since baseline’ has not been answered with Yes or No and the new lesion details are blank this is not evidence that no new lesions are present and should be treated as NE in the derivation of overall visit response.

Symptomatic progression is not a descriptor for progression of NTLs: it is a reason for stopping study therapy and will not be included in any assessment of NTLs.

Patients with ‘symptomatic progression’ requiring discontinuation of treatment without objective evidence of disease progression at that time should continue to undergo tumor assessments where possible until objective disease progression is observed.

### 3.1.2.3 Site Investigator Assessment Using RECIST 1.1: Overall visit response

Table 9 defines how the previously defined TL and NTL visit responses will be combined with new lesion information to give an overall visit response.

**Table 9 Overall Visit Responses**

Target Lesions	Non-target lesions	New Lesions	Overall Response
CR	CR or NA	No (or NE)	CR
NA	CR	No (or NE)	CR
CR	Non CR/Non PD	No (or NE)	PR
CR	NE	No (or NE)	PR
PR	Non PD or NE or NA	No (or NE)	PR
SD	Non PD or NE or NA	No (or NE)	SD
NA	Non CR/Non PD	No (or NE)	SD
NA	Non PD	NE	SD
NE	Non PD or NE or NA	No (or NE)	NE
NA	NE	No (or NE)	NE

**Table 9 Overall Visit Responses**

Target Lesions	Non-target lesions	New Lesions	Overall Response
PD	Any	Any	PD
Any	PD	Any	PD
Any	Any	Yes	PD
NA	NA	No	NED

CR Complete response, PR Partial response, SD Stable disease, PD Progression of disease, NE Not evaluable, NA Not applicable (only relevant if there were no TL/NTL at baseline), NED No evidence of disease.

### 3.1.3 Site Investigator Assessment Using RECIST 1.1 Modified for Confirmation of Progression

PFS as determined by RECIST 1.1 modified for confirmation of progression will be calculated using investigator assessments as detailed in Sections 3.1. This means that the visit response of PD must be confirmed by another visit response of PD at the next scheduled visit and no earlier than 4 weeks after the initial assessment of PD in the absence of clinical deterioration and if clinically feasible. Confirmation of progression needs to be programmatically derived.

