Disease progression for patients in the IMT treatment arms should be confirmed according to RECIST 1.1; timepoint assessments showing PD should be confirmed preferably at the next scheduled imaging visit and no earlier than 4 weeks after the preceding assessment of PD in the absence of clinically significant deterioration. Disease progression in patients in the SoC arm should be confirmed by a scan obtained no earlier than 4 weeks after the initial assessment of PD and preferably at the next scheduled imaging visit, if clinically feasible. Treatment in all arms will continue between the assessment of progression and its confirmation. Patients with rapid tumor progression or with symptomatic progression that requires urgent medical intervention (eg, central nervous system metastasis, respiratory failure due to tumor compression, or spinal cord compression) will not be eligible to continue to receive study drug.

Radiographic progression would be considered confirmed if the following criteria are met:

- $\geq 20\%$ increase in the sum diameters of target lesions compared with the nadir at 2 consecutive scan timepoints with an absolute increase of 5 mm, *and/or*
- Significant progression (worsening) of non-target lesions at the confirmatory scan timepoint compared with the first timepoint where progression of non-target lesions

was identified (Note: new lesions identified at the previous scan timepoint are considered non-target lesions at the confirmatory scan timepoint), *and/or*

- Additional new unequivocal lesions at the confirmatory scan timepoint.

In the absence of clinically significant deterioration, the Investigator should continue study treatment until progression is confirmed.

If radiographic progression is not confirmed, then the patient should continue on study treatment and on treatment assessments.

If a patient discontinues treatment (and/or receives a subsequent cancer therapy) prior to progression, then the patient should still continue to be followed until confirmed objective disease progression.

Patients with clinical evidence of progression who do not meet PD criteria by RECIST 1.1 should continue to be followed until there is radiographic documentation of PD.

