### **3. PRIMARY AND SECONDARY VARIABLES**

#### **3.1 Derivation of RECIST Visit Responses**

The analyses of the RECIST 1.1 based secondary endpoints, PFS, ORR, DoR, TTR, BoR, APF6 and APF12, will be based on site investigator assessments using RECIST 1.1. In addition, PFS2 will be defined by local clinical practice.

For all patients, the RECIST version 1.1 (see further Appendix E of the CSP) tumor response data will be used to determine each patient's visit response. It will also be used to determine if and when a patient has progressed and also their best objective response. RECIST 1.1 assessments will be performed using CT/MRI assessments of the neck (from base of skull) though the chest and abdomen (including liver). Additional anatomy should be imaged based on signs and symptoms of individual patients at baseline and follow-up.

The baseline assessments should be performed no more than 28 days before randomization and ideally should be performed as close as possible to the date of randomization (Tables 2 and 3 of CSP). Follow-up assessments will be performed every 6 weeks for the first 24 weeks (relative to the date of randomization) and then every 8 weeks as indicated in the schedule of procedures until confirmed objective disease progression per RECIST 1.1. The confirmatory scans should preferably be performed at the next scheduled visit (relative to the date of randomization) and no less than 4 weeks after the initial assessment of PD (in the absence of clinically significant deterioration). Confirmation of progression in patients in the SoC arm is preferable and should be done if clinically feasible. If an unscheduled assessment was performed and the patient has not progressed, every attempt should be made to perform the subsequent assessments at their scheduled visits (relative to the date of randomization). All confirmatory scans should be recorded in the database.

Progression would be considered confirmed if the following criteria are met:

- $\geq 20\%$  increase in the sum of diameters of target lesions (TL) compared with the nadir at 2 consecutive visits with an absolute increase of 5 mm

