The assessment of progression of  $\geq 20\%$  increase in the sum diameters of target lesions compared with the nadir is at the first progression time point relative to the nadir (the smallest sum of diameters and this may be at baseline or subsequent follow-up visit). The confirmed scan confirms the persistence of the  $\geq 20\%$  increase relative to the nadir.

- And/or clinically significant progression (worsening) of non-target lesions (NTL) or new lesions at the confirmatory PD time point compared with the first time point where progression of non-target lesions or new lesions identified
- And/or additional new unequivocal lesions at the confirmatory PD time point compared with the first time point new lesions were identified.

RECIST 1.1 will be regarded as primary in terms of the efficacy analyses and RECIST 1.1 modified for confirmation of progression assessment is supportive (Section 3.1.3).

In the absence of significant clinical deterioration, the investigator should continue study treatment until progression is confirmed.

If progression is not confirmed, then the patient should continue on study treatment and on treatment assessments. Treatment through PD in the Standard of Care group is at the Investigator's discretion; however, a confirmatory scan is required for all patients in the Standard of Care group, if clinically feasible, even if a subsequent treatment is started.

If a patient discontinues treatment (and/or receives a subsequent cancer therapy) prior to progression, then the patient should still continue to be followed until confirmed objective disease progression.

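### SAP 3.1.3 restates confirmed progression as two successive PD visits, so a new lesion that merely persists confirms itself, contrary to SAP 3.1, Protocol 5.1 and Appendix E

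*SAP*

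**What the plan says.** SAP 3.1.3 defines PFS with confirmation of progression in two steps. It first says that this PFS "will be calculated using investigator assessments as detailed in Sections 3.1". It then explains what that means: "the visit response of PD must be confirmed by another visit response of PD at the next scheduled visit", at least four weeks later, with the confirmation derived by program.

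SAP 3.1 holds lesion-level criteria, any one of which suffices:

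- a target-lesion increase of at least 20% "compared with the nadir at 2 consecutive visits with an absolute increase of 5 mm";
- "clinically significant progression (worsening) of non-target lesions (NTL) or new lesions at the confirmatory PD time point", judged against the time point at which that progression was first seen;
- "And/or additional new unequivocal lesions at the confirmatory PD time point compared with the first time point new lesions were identified".

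Protocol 5.1 and the confirmation part of Appendix E give the same three routes; the last is "Additional new unequivocal lesions at the confirmatory scan timepoint". Both add that new lesions from the previous scan count as non-target lesions at the confirmatory scan, so they have to worsen.

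For the visit response, SAP 3.1.2.2 says: "A new lesion indicates progression so the overall visit response will be PD irrespective of the TL and NTL response". Table 9 repeats this: any target and non-target response with a new lesion gives PD. The eCRF question cited in 3.1.2.2 is "Any new lesions since baseline".

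SAP 3.2.1.1 requires confirmation by the next scheduled scan without restating the lesion criteria. It counts a single PD with no further scan as PD. SAP 3.1 calls the confirmed-progression assessment supportive.

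**The concern.** The restatement in 3.1.3 is not equivalent to the section it cites. A lesion first seen at one visit is, by the wording of the eCRF question, still new since baseline at the next. The second visit is then PD whatever else has happened, and the first PD is confirmed without any worsening. Under Section 3.1 and the protocol the same patient is not confirmed.

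Two things are at stake. First, two programmers working from the same SAP could derive different PFS dates from the same data. Second, the analysis compares immunotherapy arms with chemotherapy plus cetuximab, and both documents accept that apparent progression under immunotherapy can be misleading. If one class of progression confirms itself, fewer events can be reclassified, and agreement with the main PFS analysis would be weaker evidence of robustness than it appears.

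**Working it through.** The plan gives no figure to reproduce here, so the check is one of logic: apply both rules to the same visit sequences.

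**Inputs**

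- Target-lesion response (SAP Table 7): PD if 100 × (sum − nadir)/nadir is at least 20 and sum − nadir is at least 5 mm; PR if 100 × (sum − baseline)/baseline is −30 or lower; otherwise SD (complete response does not arise here).
- Visit response (SAP Table 9): PD if target lesions are PD, or non-target lesions are PD, or a new lesion is recorded. In the sequences below it otherwise follows the target lesions.
- Rule A (literal 3.1.3): first visit PD and next visit PD.
- Rule B (SAP 3.1): target-lesion PD at both visits, or non-target or earlier new lesions worse than at the first PD, or an additional new lesion.

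**Arithmetic**, with baseline and nadir both 50 mm:

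- 65 mm: 100 × 15/50 = +30%, and +15 mm, so PD.
- 55 mm: 100 × 5/50 = +10%, so SD.
- 32 mm: 100 × (−18)/50 = −36%, so PR.

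**Eleven illustrative sequences** (target sum 50 mm at both visits unless stated):

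| Sequence | Visit responses | Rule A | Rule B |
|---|---|---|---|
| Target sum 65, then 55 mm | PD, SD | no | no |
| Target sum 65, then 32 mm | PD, PR | no | no |
| Target sum 65, then 65 mm | PD, PD | yes | yes |
| New lesion persists, not worse | PD, PD | **yes** | **no** |
| New lesion persists, not worse; target sum falls to 32 mm | PD, PD | **yes** | **no** |
| New lesion gone, question answered No | PD, SD | no | no |
| New lesion gone, question left at Yes | PD, PD | **yes** | **no** |
| New lesion worsens | PD, PD | yes | yes |
| Additional new lesion appears | PD, PD | yes | yes |
| Non-target PD, still rated PD, no further worsening | PD, PD | **yes** | **no** |
| Non-target PD reverts | PD, SD | no | no |

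The rules agree in seven sequences and differ in four. The sequences were chosen to exercise the rules, so 4 of 11 is not a frequency.

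**Direction.** All four differences go the same way: confirmed under A, unconfirmed under B. This follows from the definitions. A persisting target-lesion increase, non-target worsening rated PD, a worsening new lesion that is still present, and an additional new lesion each make the second visit PD. Whatever B confirms, A therefore confirms too.

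**Who is affected.** Patients whose first PD rests only on a new lesion or on non-target progression, who were scanned again, who did not worsen, and who had no additional new lesion. A patient with no further scan counts as PD under SAP 3.2.1.1 whichever rule is used.

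**The case against.** The best defence is the cross-reference. Section 3.1.3 points to Section 3.1, which points back to 3.1.3, so the right criteria are already cited, and the sentence about a second PD could be read as a summary of timing. It stands that the SAP contains a sound rule; the fault is a contradiction over which rule is programmed. It does not remove the problem. The restatement is offered as the meaning of the rule, it is the only form expressed in the derived visit response, and the SAP nowhere says that 3.1 prevails.

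A second defence is that the eCRF is not in the documents. If the protocol's handling of earlier new lesions as non-target lesions were carried into the program, a stable one would not make the second visit PD. That is so, but Table 9 and SAP 3.1.2.2 do not carry it over. New lesions are recorded with an assessment date, so a program could separate earlier from additional ones; 3.1.3 does not tell it to. The case of a lesion that disappears depends entirely on how the question is then answered.

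Third, the analysis is supportive and concerns a secondary endpoint with nominal p-values. That stands and limits the weight of the point.

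A reader might go further and infer that the analysis cannot detect pseudo-progression at all, or must reproduce the main PFS result by construction. The documents do not support either: rows 1, 2, 6 and 11 of the table stay unconfirmed under the literal rule. Nor do they state that this analysis is there to test pseudo-progression. They mention it when justifying treatment beyond PD (Protocol 1.4, SAP 1.2); the link to this analysis is a reasonable inference only.

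**Conclusion.** The contradiction is real. Read literally, SAP 3.1.3 confirms progression that SAP 3.1, Protocol 5.1 and Appendix E would leave unconfirmed, where a new lesion persists without worsening or non-target disease stays rated PD without further worsening. The resulting tilt is one-way, towards agreement with the main PFS analysis.

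Its size cannot be stated. The documents give neither the share of first progressions resting on new or non-target lesions alone, nor the share of those rescanned without worsening. The effect could be nil or could reach every such progression, and the hazard ratio under either rule cannot be predicted.

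The conclusion assumes that the new-lesion question is answered as worded, relative to baseline, and feeds Table 9 unchanged. It is confined to one supportive analysis of secondary PFS. The main PFS analysis, the OS analyses and the multiple testing procedure do not depend on it.

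**What to change.** In SAP 3.1.3, replace the requirement for a second PD visit with the three criteria of Section 3.1, and refer to them explicitly in the confirmation paragraph of 3.2.1.1. State that new lesions from the first PD scan are handled as non-target lesions at the confirmatory scan, as the protocol has it. Use lesion assessment dates to identify additional new lesions, so that the since-baseline question does not by itself confirm PD.

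If worsening of earlier new lesions was not captured on the eCRF, run the analysis twice: once with PD followed by PD, and once with the Section 3.1 criteria, counting earlier new lesions as not worse. These bound the set of confirmed progressions; report both hazard ratios.

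The cost is a short SAP edit and minor extra programming for one sensitivity analysis. No new data are needed and patient management does not change.

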## 3.2 Outcome Variables

All RECIST assessments, whether scheduled or unscheduled, will be included in the calculations. This is also regardless of whether a patient discontinues investigational product or receives another anti-cancer therapy. All efficacy and PRO data will be summarized and analysed using the full analysis set (FAS), refer to Table 6 for the analysis set for these variables.

### 3.2.1 Primary endpoint (OS)

OS is defined as the time from the date of randomization until death due to any cause (i.e., date of death or censoring – date of randomization + 1). Any patient not known to have died at the time of analysis will be censored based on the last recorded date on which the patient was known to be alive (SUR\_DAT, recorded within the SURVIVE module of the eCRF).

Note: Survival calls will be made following the date of data cut-off for the analysis (these contacts should generally occur within 7 days of the data cut-off). If patients are confirmed to be alive or if the death date is post the data cut-off date, these patients will be censored at the date of data cut-off. Death dates may be found by checking publicly available death registries (as applicable under local laws).

#### 3.2.1.1 Progression free survival (PFS)

PFS (per RECIST 1.1 as assessed by investigator) will be defined as the time from the date of randomization until the date of objective disease progression or death (by any cause in the

absence of progression) regardless of whether the patient discontinues from therapy or receives another anticancer therapy prior to progression (i.e., date of event or censoring – date of randomization + 1). Patients who have not progressed or died at the time of analysis will be censored at the time of the latest date of assessment from their last evaluable RECIST 1.1 assessment. However, if the patient progresses or dies after 2 or more consecutive missed visits, the patient will be censored at the time of the latest evaluable RECIST 1.1 assessment prior to the 2 missed visits (Note: NE visit is not considered a missed visit).

Given the scheduled visit assessment scheme (i.e., six-weekly for the first 24 weeks then eight-weekly thereafter) the definition of 2 missed visits will be as follows:

- If the previous RECIST assessment is  $\leq$  study day 35 (i.e. week 5) then two missing visits will equate to 13 weeks since the previous RECIST assessment, allowing for a late visit (i.e.  $2 \times 6$  weeks + 1 week for a late assessment = 13 weeks).
- If the previous RECIST assessment is  $>35$  and  $<$  study day 120 (i.e. week 17) then two missing visits will equate to 14 weeks since the previous RECIST assessment, allowing for early and late visits (i.e.  $2 \times 6$  weeks + 1 week for an early assessment + 1 week for a late assessment = 14 weeks).
- If the two missed visits occur over the period when the scheduled frequency of RECIST assessments changes from six-weekly to eight-weekly this will equate to 16 weeks (i.e. take the average of 6 and 8 weeks which gives 7 weeks and then apply same rationale, hence  $2 \times 7$  weeks + 1 week for an early assessment + 1 week for a late assessment = 16 weeks). The time period for the previous RECIST assessment will be from study days 120 to 161 (i.e. week 17 to week 23).
- From week 23 (day 162) onwards (when the scheduling changes to eight-weekly assessments), two missing visits will equate to 18 weeks (i.e.  $2 \times 8$  weeks + 1 week for an early assessment + 1 week for a late assessment = 18 weeks).

If the patient has no evaluable visits or does not have baseline data, they will be censored at Day 1 unless they die within 2 consecutive visits of baseline, then they will be treated as an event with date of death as the event date.

The PFS time will always be derived based on scan/assessment dates and not visit dates.

RECIST 1.1 assessments/scans contributing toward a particular visit may be performed on different dates. The following rules will be applied:

- For Investigator assessments, the date of progression will be determined based on the earliest of the RECIST 1.1 assessment/scan dates of the component that indicates progression.
- For BICR assessments, date of progression will be determined from the progression date (PROGSCDT) provided by the BICR progression scan dates (PROGSCDT) dates.
- When censoring a patient for PFS, the patient will be censored at the latest of the dates contributing to a particular overall visit assessment.

**Note:** For target lesions, only the latest scan date is recorded out of all scans performed at that assessment for the target lesions, and similarly for non-target lesions, only the latest scan date is recorded out of all scans performed at that assessment for the non-target lesions.

PFS based on RECIST 1.1 modified for confirmation of progression may be performed for sensitivity analysis using the algorithm described above for the RECIST 1.1, but following a modification whereby any objective disease progression must be confirmed by the next scheduled scan. The confirmatory scan must be no sooner than 4 weeks after the initial documented progression. If disease progression is confirmed (or disease progression occurs and no further scans are recorded), then the date of progression will be when it was originally observed. Patients with a single disease progression and no further tumor assessment scans will be treated as PD in the analysis. In the absence of significant clinical deterioration, the investigational site is advised to continue the patient on their randomized MEDI4736 + tremelimumab combination therapy or MEDI4736 monotherapy until progression has been confirmed. If progression is not confirmed, the patient should continue their randomized MEDI4736 + tremelimumab combination therapy or MEDI4736 monotherapy treatment and on-treatment assessments. Treatment through PD in the SoC group is at the Investigator's discretion; however, a confirmatory scan is required for all patients in the SoC group, if clinically feasible, even if a subsequent treatment is started.

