### **3.2.2 Objective response rate**

ORR (per RECIST 1.1 using investigator assessments) is defined as the number (%) of patients with at least 1 visit response of CR or PR. Data obtained up until progression, or the last evaluable assessment in the absence of progression, will be included in the assessment of ORR. Patients who discontinue study treatment without progression, receive a subsequent therapy, and then respond will not be included as responders in the ORR.

Patients who continue study treatment through progression and subsequently respond with further treatment would not be included as responders in ORR assessment. Likewise, patients on the MEDI4736 + tremelimumab combination therapy arm who progress during the monotherapy portion of the regimen and subsequently respond with the optional retreatment regimen would not be included as responders in the ORR assessment.

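### In the confirmed-progression PFS sensitivity analysis, a scan taken after the next anticancer therapy has started can cancel an observed progression

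*SAP*

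**What the plan says.** SAP 3.2.1.1 builds this analysis on the main PFS algorithm with one change: "any objective disease progression must be confirmed by the next scheduled scan". On timing it says only that "The confirmatory scan must be no sooner than 4 weeks after the initial documented progression". SAP 3.1.3 puts it in terms of derived visit responses: "the visit response of PD must be confirmed by another visit response of PD at the next scheduled visit". It has qualifiers for clinical deterioration and feasibility, but none for a change of therapy.

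The only fallback for an unconfirmed progression is the absence of later scans: "Patients with a single disease progression and no further tumor assessment scans will be treated as PD in the analysis".

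On treatment between the two scans, SAP 3.2.1.1 separates the arms. For immunotherapy, "the investigational site is advised to continue the patient on their randomized MEDI4736 + tremelimumab combination therapy or MEDI4736 monotherapy until progression has been confirmed". For SoC, treatment through progression is left to the investigator, and "a confirmatory scan is required for all patients in the SoC group, if clinically feasible, even if a subsequent treatment is started". SAP 3.1 says the same for SoC.

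On which scans count, SAP 3.2 includes all RECIST assessments and adds: "This is also regardless of whether a patient discontinues investigational product or receives another anti-cancer therapy".

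**The concern.** The analysis exists to see whether PFS conclusions survive when pseudo-progression on assigned treatment is discounted. For that, the second scan has to reflect the assigned treatment. Read together, the rules above let it reflect the next treatment instead. A patient progresses, starts a new drug, shrinks below the progression threshold by the next scan, and the first progression no longer counts. The PFS clock then runs on under a drug that is not being compared.

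If this happens more in SoC than in the MEDI4736 arm, SoC PFS is lengthened and the MEDI4736-versus-SoC hazard ratio moves up. The sensitivity result could then differ from the main PFS result for reasons unrelated to pseudo-progression, and a reader of the study report could not tell which cause was at work.

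**Working it through.** **1. Does any passage close the gap?** The plan gives no PFS event count or power to reproduce, so the first step is textual.
- SAP 3.1.3 and 3.2.1.1: confirmation depends on the next scheduled scan, at least 4 weeks later, with no link to the start of a new therapy.
- SAP 3.1.2 and 3.2: scans under another anticancer therapy are included.
- SAP 3.2.1.1: an unconfirmed progression survives only if no further scan is recorded.
- SAP 3.1 and 3.2.1.1: in SoC the scan is sought even after a switch.

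No section keeps, censors or flags a progression followed by new therapy. A program written to this text drops it if the next scan is not PD.

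**2. Is it specific to SoC?** No. The scan-inclusion rule in SAP 3.2 applies to every arm, and SAP 3.1 follows any patient who has received a subsequent therapy. SAP 3.1 and 3.2.1.1 do foresee switching in SoC and advise continuing randomised drug only in the immunotherapy arms. Against this, Protocol 5.1 and 7.2.1 state that treatment continues in all arms until confirmation. The asymmetry is therefore plausible but not established.

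**3. Size if only SoC is affected.** Share of SoC PFS events cancelled:

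c = s × r × 0.85

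Here s is the share of SoC progressors who switch before the confirmatory scan, r is the share of those not PD at that scan, and 0.85 is the share of PFS events that are radiographic. All three are assumptions. From the documents: SoC median PFS 5.5 months (Protocol 1.1.1), 190 patients per arm (Protocol 8.2) and later-line median PFS 3 months (Protocol 1.2.5). Model: exponential PFS, follow-up cut at 30 months, and each cancelled SoC event moved by 1.5 months plus an exponential time with median 3 months.

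| s, r | c | HR if true 0.80 | HR if true 1.00 |
|---|---|---|---|
| 0.30, 0.30 | 7.7% | 0.84 | 1.06 |
| 0.40, 0.40 | 13.6% | 0.88 | 1.09 |
| 0.60, 0.50 | 25.5% | 0.96 | 1.20 |

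SoC median PFS rises from 5.5 to about 6.0 to 7.1 months.

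Values of r nearer the documents' figures are smaller. MEDI4736 response rates in pretreated SCCHN were 11% overall and 18% in PD-L1-positive tumours (Protocol 1.2.1). Then c = 0.30 × 0.11 × 0.85 = 2.8% up to 0.60 × 0.18 × 0.85 = 9.2%, and a true 0.80 reads about 0.82 to 0.85. These rates are anchors, not bounds: shrinkage short of a partial response can be enough if the progression was marginal.

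**4. Size if both arms are affected.** Protocol 1.1.1 gives a 36% response rate for EXTREME, a conceivable next therapy after MEDI4736. The switching rates remain assumptions.
- SoC 40% × 11%, MEDI4736 15% × 36%: c = 3.7% and 4.6%. True 0.80 reads 0.80; true 1.00 reads 0.99.
- SoC 30% × 30%, MEDI4736 20% × 36%: c = 7.7% and 6.1%. True 0.80 reads 0.82; true 1.00 reads 1.01.

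**5. What replaces the cancelled event.** The SAP does not spell this out. The patient may have a later confirmed progression or death, or be censored at a later scan. With scans on the protocol's 6- and 8-week grid and SoC-only cancellation, a true 0.80 reads 0.82 with no cancellation because of grid rounding. At 5%, 10%, 20% and 30% cancelled it reads 0.84, 0.88, 0.95 and 1.02 if a later progression is counted. If the patient is censored it reads 0.86, 0.92, 1.07 and 1.23.

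**The case against.** **Status.** This is a supportive analysis of a secondary endpoint. PFS is outside the multiple testing procedure and receives nominal p-values only (SAP 4 and 4.1). SAP 3.2.1.1 says the analysis may be done, SAP 4.2.3 that it will be. This stands, and it limits the stakes.

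**Direction.** A reader might infer that SoC PFS is bound to be lengthened. The documents do not support that. The rule is open in all arms, no switching rates are given, and the Protocol's text on continuing treatment would, if followed, limit SoC switching before confirmation. Step 4 shows the bias vanishing when cancellation is similar in both arms. If cancellations are mainly in SoC, the bias works against MEDI4736 and so would not create a false benefit.

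**How easily a progression is cancelled.** Target-lesion progression is judged against nadir (SAP Table 7), so disease merely held stable by the next drug is still PD. Under SAP 3.1.3 with Table 9, a persisting new lesion also still gives PD. This argues for the lower part of the range. SAP 3.1, however, asks for further worsening of non-target or new lesions, or additional new lesions. On that wording a new lesion held stable would fail to confirm. The two definitions do not agree.

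**Existing fallback.** Switchers with no further scan already count as events. That is correct, but SAP 3.2.1.1 also asks for the scan after switching wherever feasible.

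**Consistency with the PFS definition.** PFS deliberately ignores subsequent therapy. That wording concerns therapy before progression; here a progression has already been observed and is removed. The ORR section does guard against crediting a later therapy, "Patients who discontinue study treatment without progression, receive a subsequent therapy, and then respond will not be included as responders in the ORR". That sentence covers patients who stop without progression, so it is an analogy rather than a contradiction.

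**Conclusion.** The gap is real and follows from stated rules: a non-PD scan under a subsequent therapy cancels a first progression in this sensitivity analysis, in any arm. Exposure is probably greater in SoC, subject to reconciling SAP 3.1 and 3.2.1.1 with Protocol 5.1 and 7.2.1.

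The size is unknown. With SoC-only cancellation of about 3% to 26% of SoC PFS events, each replaced by a later event, a true hazard ratio of 0.80 reads roughly 0.82 to 0.96. Censoring instead would move it further. Comparable cancellation in both arms leaves little or no bias. All of this rests on assumed switching and non-PD rates.

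A reader might also infer that the trial's efficacy conclusions are at risk. They are not: OS and the main PFS analysis do not use the confirmation step. The change is worth making because it is cheap and lets the analysis answer the question it was written for.

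**What to change.** Add to SAP 3.1.3 and 3.2.1.1: if a subsequent anticancer therapy, excluding palliative radiation, starts after the first RECIST progression and before the confirmatory scan, the progression is kept as an event at its original date, in all arms. The palliative-radiation exclusion matches SAP 4.1.

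Report by arm the number of unconfirmed progressions and the number of confirmatory scans taken under subsequent therapy. While editing, state how an unconfirmed progression is handled afterwards, align the two definitions of confirmation, and settle whether the analysis will be done. The Protocol and SAP passages on treatment between progression and confirmation must also be reconciled.

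The cost is one derivation rule and a short table. Start dates of subsequent therapy are already needed for TFST (SAP 3.2.7), so no new data are required. The downside is that some true pseudo-progressions in patients who switched early will count as events, more often in whichever arm switches more. The by-arm counts make that visible.
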